18. SAMPLE AND RECRUITMENT

18.1 Study Population, Sampling and Recruitment

All patients attending the dermatology department for wide local excision as part of their skin cancer treatment and primary closure of the subsequent wound will be considered for entry into the trial.

Clinicians will identify potential participants during routine practice at their clinic visit. Patients who fulfil the entry criteria will be invited at that appointment to take part and given copies of the PIS. They will also be offered a telephone appointment with a member of the research team for further information about the trial.

Alternatively, patients will be informed of the study when telephoned to confirm the time and date for their surgery. If they express interest in the study, they will be offered a further telephone call with a member of the research team to answer any questions they may have about the study and gain verbal consent. The PIS can be emailed or posted to the patient at their request.

All patients will be offered a telephone call between clinic visit and their date of surgery for any questions to be answered and verbal consent to be gained.

18.2 Inclusion Criteria

- Patients of 18 years old or above who had capacity to consent to surgery who were willing to attend follow-up appointments within the department
- Patients undergoing wide local excision as part of their skin cancer treatment pathway
- Lesions excised from the anterior chest or back
- Post-operative wound $\geq 10\text{mm}$ width

Timing of Suture Removal to Reduce Scarring in Skin Surgery

- Wound could be closed with primary intention healing

18.3 Exclusion Criteria

- Inability to provide valid informed consent and/or unwilling to attend for follow-up
- Wounds where the edges could not be closely adhered with dermal sutures alone.
- Wounds requiring a flap or graft for closure.
- Patients requiring further treatment following original excision eg. Further WLE, radiotherapy etc.

18.4 Sample Size

As this is a feasibility study, it will not be powered to find significant differences between the groups. Instead it is an opportunity to test the feasibility of collecting the specified outcome data and describing it in terms of central tendency (mean, median) and dispersion (standard deviation or interquartile range as appropriate). A feasibility study provides an excellent opportunity to uncover problems ahead of time, minimizing the need to adapt procedures or to develop contingency plans at short notice when the larger study is being conducted. A simple method for choosing a sample size for a feasibility study that ensures the discovery of potential problems with high confidence is employed here [9]. The method is used to determine the necessary sample size so that a problem is likely to be observed at least once during the course of the feasibility study. The emphasis therefore is on “problem detection” and not on the estimation of the “problem frequency.” If the probability (p) of a problem arising is 0.05, then a sample size of 59 would be required to detect at least one instance of the problem. The formula for calculating this is approx. $3/p$ participants if one wants to be approximately 95% certain that the problem will manifest itself at least once during the feasibility study. We will aim for 30 analysable cases per group in the final dataset giving a total of 60 cases.

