4. STUDY SUMMARY

Study Title	Timing of Suture Removal to Reduce Scarring in Skin Surgery
Study Design	Prospective randomized assessor blinded parallel group feasibility study
Planned Size of Sample	60
Follow up duration	3 months
Research Question/Aim(s)	In patients undergoing wide local excision and primary wound closure for treatment of skin cancer, does earlier removal of percutaneous sutures (7 days rather than 10 days) reduce the incidence of suture marks assessed at 3 months post-operatively.

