16.4 Randomization and Blinding

Timing of Suture Removal to Reduce Scarring in Skin Surgery

Patients will be randomized into two groups following acceptance into the trial. A dermatology nurse, independent to the research trial and not involved in data collection or analysis, will use a random number generator to prepare 60 sealed envelopes, labelled 'participant 1' to 'participant 60'. These sealed envelopes will contain a slip of paper that either says 'suture removal at 7 days group' or 'suture removal at 10 days group'. During preparation of these envelopes using the random number generator, an odd number produced will be 'suture removal at 7 days group' and an even number will be 'suture removal at 10 days group'. The nurse who prepares these envelopes will be independent of the research trial to avoid any selection bias and maintain concealment. They will also have completed a 'Good Clinical Practice' (GCP) certificate. The surgeon and members of the research team involved in data gathering and analysis will be blinded to allocation.

After written consent to the trial has been gained, and excision of the lesion performed, the patient will leave the theatre room alongside one of our dermatology nurses/HCAs who is independent of the research team in order to maintain concealment and prevent selection bias. The patient and nurse/HCA will open one of the sealed envelopes, in numbered order, to reveal which arm of the trial they have been allocated to. The patient will be requested not to disclose which arm of the trial they were in. The theatre nurse or healthcare assistant will then discuss the post-operative wound care and timing of suture removal with the patient.

Patient blinding is not feasible as patients need to know which day to have their sutures removed post-surgery.

Before the patient leaves the department, an appointment will be booked with their GP for suture removal at either 7 or 10 days. If their GP does not have the capacity to remove the sutures on the given day, an appointment will be booked within the dermatology department on the given day for suture removal.

If the patient cannot attend the appointment for suture removal specifically on day 7 or 10, they will be removed from the study.

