The envelope containing the slip of paper with the randomized trial arm will be re-sealed and placed in a larger envelope labelled with the participant number. The signed consent form will also be kept in this labelled participant envelope, which will be placed in a secure location in line with data governance.

Concealment of the trial arm allocation will be maintained until trial completion. However, the code could be broken in the event of a significant adverse event.

All recorded data will be anonymized prior to statistical analysis by the statistician.

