16.5 Wound Dressing and Post-operative Care

Following wound closure, the wounds will be dressed with steristrips, a sterile film and pad dressing as per protocol after skin surgery. After 48 hours, the patients will be instructed to remove the dressing and then gently cleanse the wound and apply petroleum jelly to it twice daily until suture removal. This advice will be given to all patients independent on which trial arm they have been allocated.

Timing of Suture Removal to Reduce Scarring in Skin Surgery

On the day of suture removal, either at GP or in the dermatology department, sutures will be removed as per our standard operating procedure (SOP), available in the department or emailed to the GP practice performing the suture removal (please see appendices).

If there are any signs of wound dehiscence, or that the wound may dehisce on suture removal, the suture may be kept in, as per advice on our SOP. These patients will be withdrawn from the study.

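### The plan wants 60 analysable patients (30 per group) but provides for only 60 to be randomised, so one post-allocation loss defeats the target; the allocation method as described does not guarantee 30:30 either.

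*Combined protocol and SAP*

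**What the plan says.** Section 18.4 sets the size after losses: "We will aim for 30 analysable cases per group in the final dataset giving a total of 60 cases". It derives the total from a problem of probability 0.05, for which it gives 59 patients, or about 3/p, to be roughly 95% sure of seeing the problem at least once.

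Two other places fix the number entering:

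- The row "Planned Size of Sample" in section 4 gives 60.
- In section 16.4 an independent nurse will "use a random number generator to prepare 60 sealed envelopes". The patient and a nurse or healthcare assistant "will open one of the sealed envelopes, in numbered order", after excision. The used slip "will be re-sealed and placed in a larger envelope labelled with the participant number", so a lost patient's slot is not reused.

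On the allocation itself, "an odd number produced will be" the 7-day group and an even one the 10-day group. No block, cap or fixed split is mentioned.

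Several routes lead out of the study after the envelope is opened:

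- Section 16.4: "If the patient cannot attend the appointment for suture removal specifically on day 7 or 10, they will be removed from the study".
- Section 16.5, on actual or threatened dehiscence at suture removal: "These patients will be withdrawn from the study". The suture-removal SOP (Appendix 13) also excludes patients whose sutures are kept in because the wound may dehisce.
- Section 18.6 lets patients withdraw at any time.
- Section 18.3 excludes patients who need further treatment after the original excision. If that means the study excision, the need may become known only after allocation.

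Follow-up rates and adherence are themselves objective 5 in section 14.

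**The concern.** The number to be randomised and the number to be analysable are the same, in a study that writes post-allocation removal into its procedures and sets out to measure loss. One lost patient makes 30 + 30 unattainable under the procedures described. A shortfall against 18.4 would then be a product of how the number was written and would say nothing about feasibility.

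The per-group figure has a second weakness. Section 16.4 does not say whether the nurse draws independent random numbers or puts the numbers 1 to 60 in random order. Only the second yields 30:30.

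No bias or loss of power is alleged. Section 17 makes the analysis descriptive and rules out formal comparisons. What is at stake is a stated sample size that the design does not deliver.

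**Working it through.** **Inputs.** Target 60 analysable, 30 per group (18.4); planned sample 60 (section 4); 60 envelopes (16.4); problem probability p = 0.05 (18.4). The documents give no loss rate, so every rate *l* below is an assumption. The 5% value borrows the plan's problem frequency and applies it to loss. Withdrawal because wound edges cannot be approximated (16.3) is not counted, since it occurs during surgery, before an envelope is opened.

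**1. The plan's own figure.** n = ln(1 − 0.95) / ln(1 − 0.05) = 58.40, rounded up to 59; 3/p = 3/0.05 = 60. Both reproduce.

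**2. Chance of 60 analysable from 60 randomised.** With no replacement this needs zero losses: P = (1 − l)^60, taking losses as independent.

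| Assumed loss | P(60 analysable) |
|---|---|
| 1% | 54.7% |
| 2% | 29.8% |
| 5% | 4.6% |
| 10% | 0.2% |

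At 5%, the chance of at least one loss is 1 − 0.95^60 = 95.4%.

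**3. Effect on problem detection.** P(problem seen at least once) = 1 − 0.95^n.

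| Patients observed | Detection of a 5% problem |
|---|---|
| 60 | 95.4% |
| 59 | 95.2% |
| 58 | 94.9% |
| 54 (60 × 0.9) | 93.7% |
| 48 (60 × 0.8) | 91.5% |

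The margin over the plan's own requirement of 59 is one patient. The fall at 10–20% loss is about 2 to 4 percentage points, and only for problems visible solely at the 3-month visit. Patients removed earlier still reveal problems that arise before they leave.

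**4. Arm sizes at allocation, before any loss.** If the numbers are independent draws, the 7-day arm is Binomial(60, 0.5):

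- P(exactly 30:30) = C(60,30)/2^60 = 10.3%.
- Expected smaller arm = 30 − 30 × 0.1026 = 26.9.

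If the numbers are a random ordering of 1 to 60, there are 30 odd and 30 even and the split is exactly 30:30.

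**5. Numbers needed to keep the target as written.** With equal arms, P(both arms have at least 30 analysable) = P(Bin(N/2, 1 − l) ≥ 30)². At 10% loss, N = 70 gives 75.4% and N = 72 gives 87.8%; at 20% loss, N = 82 gives 80.6%. Inflating only so that the expected total reaches 60 gives 60/0.9 = 66.7, so 67, and 60/0.8 = 75.

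**The case against.** The strongest reply is that 18.4 only aims for 60, that its calculation is correct, and that little depends on hitting the number. The analysis is descriptive, no progression rule in the available text is tied to 30 per group, and a report of, say, 54 out of 60 would be a perfectly interpretable retention result. Further envelopes could be prepared, since nothing caps enrolment at 60. The study flow chart did not survive in the available text and might address replacement. On balance, simple randomisation is valid and the cost of imbalance is small: for a difference in proportions, 27:33 instead of 30:30 widens the standard error by a factor of √[(1/27 + 1/33)/(2/30)] = 1.005, and 24:36 by 1.02.

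Much of this stands, and it limits the weight of the point. The 59 is right, detection barely moves, the loss rates are assumed, and an uneven split does no real harm to a descriptive analysis. It does not remove the inconsistency. A target should be attainable under the procedures written around it, and this one survives no losses at all. A later top-up is not described and would need its own allocation rule. A flow chart would not alter the explicit count of 60 envelopes.

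**Conclusion.** The point holds, and the plan should be changed. Section 18.4 names a final dataset that sections 4 and 16.4 deliver only if nobody is lost after allocation: a 54.7% chance at an assumed 1% loss, 4.6% at 5% and 0.2% at 10%. The 30-per-group figure also depends on an allocation detail that 16.4 leaves open; under independent draws, exact balance at allocation has probability 10.3%.

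The consequence is moderate. At an assumed 10–20% loss, detection of a 5% problem seen only at 3 months is 93.7% to 91.5% instead of 95.4%. The conclusion that one loss defeats the target needs no loss rate. It rests only on there being no replacement rule or spare envelopes, and none is stated in the text available.

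**What to change.** **Section 18.4.** Separate the two numbers, for example: *60 patients will be randomised (30 per arm). At an assumed 10–20% loss, about 48–54 will be analysable. A 5% problem observable in all 60 will be seen at least once with about 95% probability, and one seen only at the 3-month visit with about 91–94%.* The 10–20% is an assumption for the investigators to confirm or replace.

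**Section 16.4.** Have the same independent nurse prepare the 60 envelopes from a list balanced 30:30 overall, using permuted blocks of varying size in random order. Six blocks of 4 and six of 6 give 24 + 36 = 60, with 12 + 18 = 30 per arm. Block sizes should be withheld from the research team. This makes the 30-per-arm figure in the restated 18.4 true.

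**Cost.** No extra patients: one rewritten paragraph and a different list before the first envelope is opened. The stated analysable number falls from 60 to about 48–54. Blocks add slight predictability, limited by the varying withheld sizes, by opening the envelope after excision, and by the surgeon being blinded to allocation.

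Keeping 30 + 30 analysable with at least 80% probability would instead need 72 randomised at 10% loss or 82 at 20%, that is 12 to 22 more patients. The problem-detection rationale does not justify that, so it is not proposed.

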18.5 Sample Identification

As mentioned previously, all patients attending the dermatology department for wide local excision as part of their skin cancer treatment will be considered for entry into the trial. Only the members of the existing clinical care team will have access to patient records in order to identify potential participants during their clinic visit. Any patients that have been informed of the study whilst having the time and date of their surgery confirmed, and have expressed interest, will be offered a further telephone call to discuss the study in depth and have any questions answered.

18.6 Consent

All patients who express interest in the study will be given the patient information leaflet either in physical form, post or email. They will be invited to discuss the project further with a member of the research team by means of a telephone call between their clinic attendance and surgical

Timing of Suture Removal to Reduce Scarring in Skin Surgery

appointment. Participants will be given sufficient time to read the information sheet and ask any further questions prior to consenting. Verbal consent will be gained on the telephone.

Participants willing to join the trial will have written informed consent obtained by a member of the research team at the time of their surgery attendance. A electronic copy of this research consent will be placed on the participants electronic hospital record. Only once they are fully informed will they be asked to make a decision to enter the trial.

The patient will be informed that they do not have to take part in the study and if they choose not to take part, refusal to enter into the study will not compromise their care.

The patient will also be informed that if at any time they wish to withdraw from the study they can do so, without having to give a reason and again this will not compromise their care.

The patient's GP will be informed by letter of the patient's inclusion in the study.

If any new information becomes available which may be relevant to the patients consent, forms will be revised and informed consent sought again.

Once the decision to take part has been agreed, randomization will occur.

Please seen appendix for patient information leaflets and consent documents.

19. ETHICAL AND REGULATORY COMPLIANCE

19.1 Patient Safety and Serious Adverse Events

A serious adverse event (SAE) is any untoward medical occurrence that:

- Results in death;
- Is life-threatening;
- Requires inpatient hospitalization or prolongation of existing hospitalization;
- Results in persistent or significant disability/incapacity;
- Consists of a congenital anomaly or birth defect.

Adverse events (AE) that may occur and for which patients will be consented include:

- Bleeding
- Infection
- Scarring
- Wound dehiscence
- Pain

We do not anticipate there being any increase in adverse events in either arm. The aim of the study is to assess whether early suture removal reduces scarring. It may become apparent that scarring is

Timing of Suture Removal to Reduce Scarring in Skin Surgery

less in the early suture removal arm. We will record the incidence of adverse events in both treatment arms to ensure that patients are not experiencing a greater number of adverse events in either treatment group

This is a pragmatic trial: the nature of the study means that it involves routine clinical practice. There should be no additional risk to patients beyond routine care. With good participant information and subsequent post-trial engagement, we would hope to recruit rapidly to the trial.

All AE's and SAE's will be reported to R&D within 24hrs of the investigator being made aware of the event. An SAE occurring to a participant will be reported to the REC that gave a favourable opinion of the study where the event was related or unexpected. This will be reported within 15 working days.

19.2 Assessment and Management of Risk

The principle investigators have a professional obligation to closely monitor participants and in the event of an adverse event being identified, follow established clinical treatment or referral protocols.

19.3 Quality Assurance Procedures

The study will be monitored in accordance with the current approved protocol and good clinical practice. Surgical technique, methodology and outcome will all be monitored and audited in accordance with current departmental practice.

19.4 Research Ethics Committee (REC) Review and Reports

Before the start of the study, a favourable opinion will be sought from a REC for the study protocol, informed consent forms and other relevant documents.

Substantial amendments that require review by NHS REC will not be implemented until that review is in place and other mechanisms are in place to implement at site. All correspondence will REC will be retained.

It is the Chief Investigator's responsibility to produce the annual reports as required and they will notify the REC at the end of the study. An annual progress report will be submitted to the REC within 30 days of the anniversary date on which the favourable opinion was given, if the study has not been declared ended by then.

If the study is ended prematurely, the Chief Investigator will notify the REC including the reasons for the premature termination.

Within one year after the end of the study, the Chief Investigator will submit a final report with the results, including any publications/abstracts, to the REC.

Timing of Suture Removal to Reduce Scarring in Skin Surgery

19.5 Amendments

If any substantial amendments to the protocol or supported documents is required, a notice of amendment will be submitted to the REC.

19.6 Protocol Compliance

Any deviations from the planned protocol will be documented and reported to the Chief Investigator and Sponsor immediately.

19.7 Data Protection and Confidentiality

The patients will be recruited to the trial and all data will be stored anonymously against a participant number. Only the clinical team will have access to the single table correlating patient name and participant number. This information will not be shared. All clinical and routine data will be collected and placed in a database by the clinical team preserving anonymity throughout the trial. It has been considered that the feasibility trial may begin to demonstrate clear advantages of one technique over the other. However, with the patient numbers involved, it seems unlikely that differences in the technique will be observed at levels that are statistically significant.

Data will be stored for 5 years then destroyed appropriately.

All paper and electronic data will be collected and stored in compliance with data protection guidelines, good clinical practice in research guidance and Trust clinical governance policy.

Please see 'Data Analysis Methods' for further information.

19.8 Access to the Final Study Dataset

The final data set will be able to be accessed by the Chief Investigator and Principle Investigators.

20. DISSEMINATION POLICY

On completion of the study, the data will be analysed and tabulated and a final study report will be prepared and issued to the Chief Investigator and Principle Investigator. Based on the results of this feasibility study, we may be in the position to write a grant proposal in order to conduct a definitive RCT in the future.

20.1 Authorship

Those who participated in study design, execution and analysis will be granted authorship

Timing of Suture Removal to Reduce Scarring in Skin Surgery

22. APPENDICES

22.1 Appendix 1 - Required Documentation

- CV's of research team
- Patient information sheet
- Patient informed consent form
- Data collection form
- POSAS Observer Scale
- POSAS Patient Scale

Timing of Suture Removal to Reduce Scarring in Skin Surgery

- VAS scale
- Standard Operating Procedure (SOP) for suture removal

22.2 Appendix 2 - Amendment History

Protocol version no.	Date issued	Author(s) of changes	Details of changes made
v1	June 2021	[name]	Protocol for submission
V2	19 th Sep 2021	[name]	Protocol updated with REC comments

